| Post-COVID-19 Functional Status Scale (PACS- CFS patients only)  |                   | X   |                              |                 |                 |                 |                 |                 |                 |                 |                    |     |           | X    | X   | X     | X    |
| COMPASS-31   |                   | X   |                              |                 |                 |                 |                 |                 |                 |                 |                    |     |           | X    | X   | X     | X    |
| Physical assessment (-), hand grip strength)   | X                 |                  |                              |                 |                 |                 |                 |                 |                 |                 |                    | X   |           |                   | X                |                    | X    |
| 6 Minute Walking Test (6MWT)   |                   | X                |                              |                 |                 |                 |                 |                 |                 |                 |                    |     |           |                   | X                |                    |                   |
| Schellong Test   |                   | X                |                              |                 |                 |                 |                 |                 |                 |                 |                    | X   |           |                   | X                |                    | X     |
| Detailed neuropsychiatric examination (optional), VLMT, BMVT-R, WAIS-IV, TAP, LPS 50+, TMT-A / B, RWT, WST |                   | X                |                              |                 |                 |                 |                 |                 |                 |                 |                    |     |           |                   | X                |                    |                   |

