### Clinical effectiveness related endpoints

- Chalder Fatigue Scale (Chalder et al., 1993) at End of Treatment (EOT) visit and at month 1, 4, and 6 after the completion of IA
- Post-COVID-19 Functional Status (PCFS) scale (Klok et al., 2020) at month 1, 2, 4, and 6 after IA completion (only in patients with PACS-CFS)
- the SF-36 physical domain (Ware & Sherbourne, 1992) at EOT visit and at month 1, 2, 4, and 6 after IA completion
- Fluge questionnaire (Fluge et al., 2011; Fluge et al., 2015) at month 1, 2, 4, and 6 after IA completion
- PEM frequency, strength and severity by PEM questionnaire (Cotler et al., 2018) at EOT visit and at month 1, 2, 4, and 6 after IA completion
- the Bell disabling scale (Bell, 1995) at EOT visit and at month 1, 2, 4, and 6 after IA completion
- the Compass-31 questionnaire (Sletten et al., 2012) at month 1, 2, 4, and 6 after IA completion
- Schellong Test (Fanciulli et al., 2019) at EOT visit and at month 2 and optional month 6 after IA completion
- hand grip strength test, at EOT and at month 2 and optional at month 6 after IA completion
- the 6 Minute Walking Test (6 MWT) ("ATS statement: guidelines for the six-minute walk test," 2002) at month 2 after IA completion
- optional neuropsychiatric assessment at month 2 after IA completion

- neurocognitive assessments (MoCA and SDMT) (Nasreddine et al., 2005) (Strober et al., 2020) at month 2 after IA completion
- quality of life (QoL) determined by the PROMIS questionnaire at month 1, 2, 4 and 6 after IA completion (Cella et al., 2019; Yang et al., 2019)
- PROMIS cognitive function short form 4a
- VLMT (verbal learning and memory test) (Helmstaedter et al., 2001)
- BVMT-R (brief visuospatial memory test revised) (Benedict, 1997)
- WAIS-IV (Wechsler adult intelligence scale) (Wechsler, 2008)
- TAP (Test of attentional performance) (Zimmermann & Fimm, 2004)
- LPS 50+ (Leistungsprüfungssystem (performance testing system) for 50 to 90 years old) (Sturm et al., 2015)
- TMT-A / B, Trail Making Test A / B (Reitan & Wolfson, 1993)
- RWT, Regensburger Wortflüssigkeits-Test (Regensburg Word Fluency Test) (Aschenbrenner et al., 2000)
- WST, Wortschatz-Test (Vocabulary test) (Schmidt & Metzler, 1992)

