| WAIS-IV (Wechsler adult intelligence scale)     | wais_0011 – wais_0070 | forward : number of correctly repeated number sequences; backwards : number of number sequences correctly recited backwards; sequential : number of correctly sequenced number sequences.  |
| TAP (Test of attentional performance)           | tap_0011 – tap_0100   | median of the reaction time. (runs without warning tone); standard deviation of the reaction  |

|  |  |   |
|--|--|---|
|  |  | time. (runs without warning tone); number of omissions in the sustained attention task; number of omissions of auditory stimuli; number of omissions of visual stimuli. |
| LPS 50+
(Leistungsprüfungssystem
(performance testing
system) for 50 to 90 years
old)  | lps_0010 – lps_0040  | number of correctly solved lines.   |
| TMT-A / B, Trail Making
Test A / B  | tmt_0011 – tmt_0060  | number of seconds to complete the task A; number of seconds to complete the task B; TMT B/A ratio = time TMT-A / time TMT-B   |
| RWT, Regensburger
Wortflüssigkeits-Test
(Regensburg Word
Fluency Test)  | rwt_0011 – rwt_0080  | number of animals or first names mentioned within 60 seconds; number of S-words or M-words mentioned within 60 seconds.   |
| WST, Wortschatz-Test
(Vocabulary test)  | wst_0010-wst_0050  | raw score (sum of correct values)   |
| Biomarker related
endpoints   |  |   |
| biomarkers of
autoimmune activity
(autoantibody titers
against neurotransmitter
receptors; among others
β2-adeno-receptor- and
muscarine- receptor-
antibodies),
autoantibodies against
known or unknown
neuronal epitopes | stoe_0023-stoe_0025, ak_0011-ak_0063                       |   |
| immunostatus (differential
blood, IgG, IgM, IgA
fractions)   | ig_0011-ig_0063  |   |
| immunoglobulin levels
(including SARS-CoV-2
antibody titers and PCR, if
applicable)   | inf_0121-inf_0140, imh_0011, imh_0012, ig_0011-
ig_0023 |   |

|  |  |  |
|--|--|--|
| inflammatory biomarkers in blood (CRP, ferritin, MBL, white blood cell count, complement factors, immunoglobulin level and subtype)  | inf_0161-inf_0173  |  |
| neurofilament (NFL)  | liq_0161-liq_0163, liq_0171-liq_0173   |  |
| auto-antibody and vaccine titers in serum and cerebrospinal fluid as well as intrathecal synthesis (CFS)   | ak_0011-ak_0063  |  |

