## 8 Handling of missing values

Missing data will be categorized according to Rubin as “missing completely at random”, “missing at random” and “missing not at random” (MCAR, MAR and MNAR) (RUBIN, 1976). For missing data in outcome variables, data will be imputed using multiple imputation by chained equations (mice) (Van Buuren & Van Buuren, 2012) with the R package MICE (van Buuren & Groothuis-Oudshoorn, 2011) with 30 imputed data sets, where appropriate is the assumption of MAR or MCAR is reasonable. It is planned to perform sensitivity analyses, in which the robustness of the inference will be investigated. Sensitivity analyses will be done using complete data without any imputation. The following variables will be used for the imputation process: all outcome variables, demographic variables age, sex, and BMI.

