### 9.3 Secondary analyses

For all secondary endpoints, descriptive statistics will be calculated and presented at each time point of measurement for both treatment groups. For continuous secondary outcomes, this will include the mean, standard deviation, median, interquartile range, minimum, and maximum. For categorical or ordinal secondary outcomes, frequencies and percentages will be reported. These descriptive summaries will be presented in tabular format, and appropriate graphical representations, such as line plots for longitudinal data, bar charts, or box plots, will be utilized to visually depict trends, distributions, and differences between treatment arms across all assessment time points. For all secondary endpoints, analysis of

covariance (ANCOVA) models will be employed, analogous to the approach for the primary outcome. The choice of link function will be tailored to the specific nature of each outcome variable (e.g., linear for continuous outcomes, binary logistic for dichotomous outcomes, or ordinal for ordered categorical outcomes). In instances of repeated measures, mixed-effects regression models will be utilized, incorporating random intercepts for individual participants to account for within-subject correlation. Each model will include the respective baseline value of the endpoint, age at baseline, and treatment group as fixed effects. Effect estimates for the treatment variable, along with their 95% confidence intervals (CI), will be reported. All analyses will be conducted using the Full Analysis Set (FAS). Sensitivity analyses will be performed using the Per-Protocol Set (PPS), without imputation of missing values, to assess the robustness of the findings.

**Responder analysis:** Explorative analyses comparing responders and non-responders in both groups regarding PCS-associated signature at baseline: CD11c and IgM expression and an aCSM frequency. For this analysis a binary logistic regression model will be implemented with the responder (yes/no) variable as the dependent variable, the PCS-associated signature at baseline, the group and the interaction term between PCS-signature at baseline and group as independent variables.

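### SAP Table 5 names a TMT B/A ratio but defines it as A divided by B, and nothing else in the SAP says which is meant

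*SAP*

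**What the plan says.** Table 5 (SAP Section 7.3) lists three Trail Making Test quantities among its additional secondary outcomes. Two are raw times: "number of seconds to complete the task A; number of seconds to complete the task B". The third is derived from them: "TMT B/A ratio = time TMT-A / time TMT-B".

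Section 9.3 applies baseline-adjusted models to all secondary endpoints: "Each model will include the respective baseline value of the endpoint, age at baseline, and treatment group as fixed effects". It then states: "Effect estimates for the treatment variable, along with their 95% confidence intervals (CI), will be reported". The ratio therefore enters its model twice, as outcome and as baseline covariate.

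The test is part of a battery that the schedule of assessments (Section 4, Table 1) marks as optional: "Detailed neuropsychiatric examination (optional), VLMT, BMVT-R, WAIS-IV, TAP, LPS 50+, TMT-A / B, RWT, WST". The endpoint list in Section 7.3 agrees: "optional neuropsychiatric assessment at month 2 after IA completion".

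**The concern.** The name and the only formula for this variable contradict each other within one table cell. A programmer who follows the formula delivers A/B under the name B/A. One who follows the name departs from the written derivation. A SAP is meant to close off that choice before the data are analysed.

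A reader of the results would depend on the name. Table 5 gives a direction for some scales, such as the Bell score and the Fluge items, but none for this ratio. If the formula were used and the name kept, a fall in the ratio actually computed would be read as a fall in its reciprocal, and the reported treatment effect could be interpreted in the wrong direction.

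**Working it through.** **Inputs.** The label (B/A) and the formula (A/B) both come from Table 5. The SAP gives no TMT times or ratios, so every numerical value below is an assumption chosen for illustration. There is no stated figure to reproduce.

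**Does anything else in the SAP settle it?**

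| Place in the SAP | What it gives |
|---|---|
| Section 1, abbreviations | Test name only |
| Section 4, Table 1 | Test name only |
| Section 7.3, endpoint list | Test name only |
| Section 7.3, Table 5 | Label B/A, formula A/B |
| Section 12, list of changes | Ratio not mentioned |
| Section 14.2, sample tables | Ratio not mentioned |

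In the first three rows the slash separates the two parts of the test and does not denote a quotient. Nothing decides between label and formula.

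**Relation between the two readings.** Let x = B/A and y = A/B. Then y = 1/x, which is strictly decreasing for x > 0. The readings agree only when the two times are equal. Assumed times of A = 30 s and B = 75 s give 75/30 = 2.50 by the label and 30/75 = 0.40 by the formula.

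It follows that:
- min(y) = 1/max(x) and max(y) = 1/min(x);
- median(y) = 1/median(x) when the number of patients in the group is odd.

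Check on x = {1.6, 2.0, 2.5, 3.1, 4.2}: y has minimum 1/4.2 = 0.238, median 1/2.5 = 0.400 and maximum 1/1.6 = 0.625.

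**Effect on a difference in medians (intervention minus control, assumed medians).**

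| Control B/A | Intervention B/A | Difference on B/A | Difference on A/B | Size ratio |
|---|---|---|---|---|
| 2.0 | 1.8 | -0.20 | 0.556 - 0.500 = +0.056 | 3.6 |
| 3.0 | 2.8 | -0.20 | 0.357 - 0.333 = +0.024 | 8.4 |
| 4.0 | 3.8 | -0.20 | 0.263 - 0.250 = +0.013 | 15.2 |

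With an odd number of patients in each group, the sign of a median difference always reverses. The change in size depends on where the ratios lie, so no single factor converts one result to the other.

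**Effect on a difference in means.** The planned models estimate adjusted means, and for means the sign need not reverse.
- Log-normal B/A with medians 2.2 and 2.5 and log-SD 0.3 in both groups (simulated): difference -0.31 on B/A and +0.057 on A/B. The sign reverses.
- Log-normal B/A with equal medians of 2.4 and log-SD 0.2 and 0.5 (simulated): difference -0.27 on B/A and -0.047 on A/B. The sign is kept.
- By hand, {1, 4} against {2.4, 2.4}: on B/A, 2.5 - 2.4 = +0.10; on A/B, (1 + 0.25)/2 - 1/2.4 = 0.625 - 0.417 = +0.21. The sign is kept.

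A model estimate on one scale therefore cannot be turned into the other from summary statistics. The analysis has to be rerun from the patients' times.

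**The case against.** The best reply is that very little hangs on this. It is one inverted fraction for one of three TMT quantities in an optional battery. Both raw times are reported separately, so either ratio can be rebuilt for every patient and no information is lost. The primary model in Section 9.2 and the precision calculation in Section 4.2 do not use the ratio. Section 9.3 also requires full descriptives ("For continuous secondary outcomes, this will include the mean, standard deviation, median, interquartile range, minimum, and maximum"), so a careful reader could normally see that the ratio does not fit the two times beside it. All of this stands, and it limits the point to a minor one.

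It can also be said that the formula is explicit and would simply be programmed, leaving only a mislabelled row, and that B/A might be a loose name for the ratio of the two parts. The first is a fair account of what would probably happen, but a mislabelled row that reverses the direction is the problem. The second is weak, because a B/A ratio is naturally read as B over A.

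Two further limits are accepted. The group differences shown rest on assumed values, and a guaranteed sign change applies to medians in odd-sized groups, not to the adjusted means that the SAP will report. And only the SAP was checked; the protocol was not available and may define the ratio.

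**Conclusion.** The point holds as a minor error. The SAP's name and formula for this outcome are reciprocals, and the SAP contains nothing that reconciles them. That conclusion needs no assumption.

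The size of the consequence does. If B/A values lay between 2 and 4, the written formula would show them as 0.25 to 0.50, and a treatment difference would usually carry the opposite sign. The number of patients who take the optional battery is unknown, so no statement about precision is made.

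No effect on the primary result is claimed. The ratio falls within the imputation list in Section 8 ("The following variables will be used for the imputation process: all outcome variables, demographic variables age, sex, and BMI"), but that is only a reason to define it consistently.

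**What to change.** Before analysis, make the name and formula in Table 5 agree, in one of two ways:
- correct the formula to time TMT-B / time TMT-A, which matches the SAP's own label; or
- keep the formula and rename the variable TMT A/B ratio.

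Use the chosen version for the outcome, the baseline covariate and, if the ratio enters it, the imputation model. It would help to state in the same cell which direction means better performance.

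The cost is one line in Table 5. Both times are already recorded, so no new data are needed.

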## 8 Handling of missing values

Missing data will be categorized according to Rubin as “missing completely at random”, “missing at random” and “missing not at random” (MCAR, MAR and MNAR) (RUBIN, 1976). For missing data in outcome variables, data will be imputed using multiple imputation by chained equations (mice) (Van Buuren & Van Buuren, 2012) with the R package MICE (van Buuren & Groothuis-Oudshoorn, 2011) with 30 imputed data sets, where appropriate is the assumption of MAR or MCAR is reasonable. It is planned to perform sensitivity analyses, in which the robustness of the inference will be investigated. Sensitivity analyses will be done using complete data without any imputation. The following variables will be used for the imputation process: all outcome variables, demographic variables age, sex, and BMI.

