After the last IA cycle, a blood sample for immunoglobulin titers is collected, the peripheral venous access (or Shaldon catheter) is removed and patients are discharged from the hospital if the investigator has no concerns. At EOT visit, patients will also complete the Chalder Fatigue Scale (Chalder et al., 1993), Fluge Score (Fluge et al., 2011; Fluge et al., 2015), and PEM questionnaires. In addition, patients will be instructed how to complete all of the requested questionnaires at home at follow up time points. If the IA treatments are performed according to the planned schedule, the end of treatment visit (EOT) will take place on Day 10. However, the EOT visit may vary between Day 9 and 12. If treatment needs to be terminated, the EOT can occur as early as day 2. In such cases, all examinations originally scheduled for day 10 will be conducted on the corresponding day. In addition, two of the four follow-up visits scheduled at month 2 (Day 60) and month 6 (Day 180; EOS, End of Study visit) will take place at the neurological wards and outpatient clinics respectively. Patients will be asked to bring all requested questionnaires (including Chalder Fatigue Scale), which they completed at home, to both follow-up visits, where further assessments and laboratory tests will be conducted. An optional second cerebrospinal fluid sample may also be taken on Day 60. The remaining two follow-up visits, scheduled at month 1 (Day 30) and month 4 (Day 120), will be conducted via telephone. During these visits, patients will be asked about any adverse events (AEs), concomitant medications, and questionnaires.

Figure 1 Schematic illustration of the study design

[figure not shown]

Table 1: Schedule of Assessments

| Period/Visit name  | SCR               | BL  | Treatment period (inpatient) |                 |                 |                 |                 |                 |                 |                 |     | Follow-up |                   |                  | EOS                |                         |
|--|-------------------|------------------|------------------------------|-----------------|-----------------|-----------------|-----------------|-----------------|-----------------|-----------------|-----|-----------|-------------------|------------------|--------------------|-------------------------|

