| Blood samples for monitoring of coagulation  | X   | X                |   |                 |                 |                 |                 |                 |                 |                 | X   |    | X                 |                  |                    |                   |
| Monitoring of IA (IgG)   |                   |                  | Before each and after last IA treatment     |                 |                 |                 |                 |                 |                 |                 |     |    |                   |                  |                    |                   |
| Blood samples for immunoglobulin titers (IgA, IgG, IgM)  |                   | X                |   |                 |                 |                 |                 |                 |                 |                 | X   |    | X                 |                  |                    | X                 |
| Adverse event questioning  |                   | X                | < ----- >                                   |                 |                 |                 |                 |                 |                 |                 |     |    |                   |                  |                    |                   |
| Concomitant Medications  |                   | X                | < ----- >                                   |                 |                 |                 |                 |                 |                 |                 |     |    |                   |                  |                    |                   |
| Procedures  |                   |                  |   |                 |                 |                 |                 |                 |                 |                 |     |    |                   |                  |                    |                   |
| Randomization  |                   | X                |   |                 |                 |                 |                 |                 |                 |                 |     |    |                   |                  |                    |                   |
| PVA or Shaldon catheter implementation   |                   |                  | X   |                 |                 |                 |                 |                 |                 |                 |     |    |                   |                  |                    |                   |

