## 4.2 Power consideration

In this study, a total of 66 patients (allocated in a 2:1 ratio: immunoabsorption (IA) group: 44 patients vs. sham group: 22 patients) will be included. Limited data from 2 small pilot studies, investigating IA in 10 patients with CFS/ME, is available to date. Consequently, data is lacking about precise effects, clinical outcomes, and effect sizes in this group of patients.

The justification of the sample size is based on the primary endpoint (change from baseline of the Chalder Fatigue Scale). The Chalder Fatigue Scale measures fatigue in patients using the overall score (range from 0 to 33) derived from a questionnaire with 11 questions (each scored from 0 to 3, see (Cella & Chalder, 2010; Chalder et al., 1993) for more details). Based on Cella & Chalder 2010, the mean score in a population of patients

suffering from CFS is 24.4 (with a standard deviation of 5.8) and for a healthy sample a mean value of 14.2 (with a standard deviation of 4.6) was observed. A difference of 10 points cannot be expected in this study since only patients suffering from CFS are included. In the systematic review of Nordin et al. 2016 a minimal important difference for the global change ranges between 2.3 and 3.3.

In an earlier study (Cleare et al. 1999) examining the efficacy of various treatments for CFS/ME, the difference in means of the Chalder Fatigue Scale was 4.5 points (Likert score) between the active and the control group. However, no sham-controlled study evaluating the effect of IA on CFS/ME has been conducted so far, but first pilot studies suggest a positive effect of IA in patients with CFS/ME.

To explore the expected precision obtained from the planned study, the distance from the mean group difference of the primary endpoint (change from baseline in Chalder Fatigue Scale) to the limits is calculated using its 95% confidence interval (CI) and a common standard deviation of 5.8 as provided for patient with CFS/ME in (Cella & Chalder, 2010). Using these assumptions and the given group sample sizes of 44 patients and 22 patients, the distance from mean to the limits of the 95%-CI is 3.03 points in the Chalder Fatigue Scale. Assuming an expected drop-out rate of 20% (resulting in expected group sample sizes of 35 and 18 patients, respectively) the distance from the mean to the limits of the 95%-CI increases to 3.37 points in the Chalder Fatigue Scale.

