### 5.2 Application

The primary analysis is performed using the full analysis set (FAS), including the estimated values from multiple imputations for missing values. An analysis of the primary outcome using the PPS is used as a sensitivity analysis. All safety analyses will be done using the SAS (Safety analysis set).

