***Biomarker related endpoints:***

- biomarkers of autoimmune activity (autoantibody titers against neurotransmitter receptors; among others  $\beta$ 2-adeno-receptor- and muscarine- receptor-antibodies) in blood at month 2 and 6 and optional in cerebrospinal fluid at month 2 after IA completion
- immunostatus (differential blood, IgG, IgM, IgA fractions) in blood at EOT, at month 2 and 6 after IA completion
- immunoglobulin levels (including SARS-CoV-2 antibody titers and PCR, if applicable) at month 2 and 6 in blood and optional in cerebrospinal fluid at month 2 after IA completion
- inflammatory biomarkers in blood (CRP, ferritin, MBL, white blood cell count, complement factors, immunoglobulin level and subtype) at month 2 and 6 after IA completion
- autoantibodies against known or unknown neuronal epitopes (Stöcker- autoimmune-encephalitis panel and screening via immunofluorescent staining on mouse brain sections – in cooperation with separate project EA1/258/18) in blood and optional in cerebrospinal fluid after IA completion .
- neurofilament (NFL) in cerebrospinal fluid at month 2 after IA completion
- auto-antibody and vaccine titers in serum and cerebrospinal fluid as well as intrathecal synthesis (CFS) at month 2 after IA completion
- inflammatory biomarkers in cerebrospinal fluid (white cell count, total protein, CSF/serum quotients of albumin (Qalb), lactate, oligoclonal IgG bands (OCB), cytokines)) at month 2 after IA completion
- MRI parameter: grey matter volume, white matter volume, thalamus volume left and right, thalamic functional connectivity to sensomotoric cluster left and right, thalamic functional connectivity to visuo-occipital cluster left and right, EndoPAT Reactive Hyperemia Index (RHI). Volumetry is based on a high-resolution T1-weighted MPRAGE sequence (voxel size 1 mm isotropic, FOV 256 mm, TR = 2500 ms, TE = 2.64 ms). The functional connectivity measures are derived from a BOLD-sensitive resting-state EPI sequence (720 volumes, voxel size 2 mm isotropic, TR = 800 ms, TE = 37 ms, FOV 208 mm).
- OCT parameter: ganglion cell-inner plexiform layer (GCIPL), peripapillary retinal nerve fiber layer (pRNFL), foveal avascular zone (FAZ), vessel density
- CD11c-Expression: Mean fluorescence intensity (MFI) on total CD19 $^{+}$  B cells, Percentage of CD11c $^{-}$  cells within the CD19 $^{+}$  gate, CD11c MFI and %CD11c $^{-}$  specifically on IgD $^{-}$ CD27 $^{+}$  memory B cells (CD19 $^{+}$ IgD $^{-}$ CD27 $^{+}$  gate)

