### 9.2 Primary analysis

For the primary outcome, the Chalder Fatigue Scale at 2 months, descriptive statistics will be presented for both treatment arms. This will include the number of participants (n), mean, standard deviation (SD), median, interquartile range (IQR), minimum, and maximum for the continuous total score. Additionally, for the categorical responses (e.g., presence/absence of fatigue), frequencies and percentages will be reported.

Confirmatory analysis of the primary outcome will be conducted based on the full analysis set. An analysis of covariance (ANCOVA) will be conducted. The dependent variable is the Chalder Fatigue Score at day 60, independent variables include baseline Chalder Fatigue Score, treatment group (intervention / control), and age at baseline. The effect estimate for the treatment variable and the corresponding 95%CI will be reported. Sensitivity analysis will be done using the PPS without imputation of missing values.

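### The imputation model for the primary analysis leaves out treatment group, so a real Day-60 Chalder effect is shrunk toward zero wherever Day-60 scores are missing

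*SAP*

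**What the plan says.** SAP section 5.2 bases the primary analysis on the full analysis set, "including the estimated values from multiple imputations for missing values". Section 9.2 calls this analysis confirmatory and specifies an ANCOVA of the Day-60 Chalder score whose "independent variables include baseline Chalder Fatigue Score, treatment group (intervention / control), and age at baseline". The result is the coefficient of treatment group.

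Section 8 prescribes chained equations "with 30 imputed data sets, where appropriate is the assumption of MAR or MCAR is reasonable", and then gives the predictors: "The following variables will be used for the imputation process: all outcome variables, demographic variables age, sex, and BMI". Treatment group is neither an outcome nor a demographic variable. Sections 5.2, 9.2, 9.3 and 11 also touch on imputation, and none of them adds treatment group or asks for imputation within arm.

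The analyses without imputation (complete data in section 8, per-protocol set in section 9.2) are sensitivity analyses only.

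**The concern.** The imputation model is narrower than the analysis model, and the missing variable is the one whose coefficient is reported. A programmer who follows section 8 fits one regression across both arms and fills in sham and active patients from the same prediction. Any arm difference among the imputed scores must then come through other observed outcomes that differ between arms. Where those are absent or weak, the imputed patients dilute the contrast.

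At stake are the main estimate and confidence interval of a small trial. The error works against an effective treatment; it does not create a false effect.

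**Working it through.** **Inputs from SAP section 4.2.** 44 and 22 patients; SD 5.8; 20% drop-out, leaving 35 and 18; a 4.5-point difference from an earlier trial of other treatments; a minimal important difference of 2.3 to 3.3. The SAP gives no power and no between-visit correlation.

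**Step 1: the plan's own figure.** Half-width = t(0.975, n1+n2−2) × 5.8 × √(1/n1+1/n2).
- 44 and 22: 1.998 × 1.514 = 3.03, as stated.
- 35 and 18: 2.008 × 1.682 = 3.377, stated as 3.37.

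**Step 2: closed form.** Let f be the share missing at Day 60, δ the true effect and D the arm difference carried by the imputed scores. The expected estimate is (1−f)δ + fD. With arm in the imputation model, D = δ. Without it:
- *Only baseline informative.* Randomisation balances baseline, so D = 0. At f = 0.20: 0.80 × 4.5 = 3.60; 0.80 × 3.3 = 2.64; 0.80 × 2.3 = 1.84.
- *EOT IgG separated by d SD, unrelated to Chalder within arm.* With 2:1 allocation the arm indicator has variance 2/3 × 1/3 = 2/9, and the proportional loss is f/(1 + (2/9)d²). For d = 1, 2, 4: 0.20/1.222 = 16%; 0.20/1.889 = 11%; 0.20/4.556 = 4%.
- *EOT Chalder carrying the full effect* (assumed correlations: 0.5 with baseline, 0.6 between later visits). Given baseline, in SD² units, the covariance is 0.60 − 0.25 = 0.35, the variance 1 − 0.25 = 0.75, and the between-arm part (2/9)(4.5/5.8)² = 0.134. Slope = 0.484/0.884 = 0.547; D = 0.547 × 4.5 = 2.46; estimate = 3.60 + 0.20 × 2.46 = 4.09, a 9% loss.

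**Step 3: simulation.** Assumptions: SD 5.8 and the correlations above; 9 of 44 and 4 of 22 Day-60 scores missing completely at random; age, sex and BMI unrelated to outcome; Bayesian linear-regression imputation (the SAP names no mice method); 30 imputations; the ANCOVA of section 9.2; 2000 runs. Monte Carlo SE is about 0.03 per mean. True effect 4.5:

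| Informative data in patients missing Day 60 | Without arm | With arm | Loss |
|---|---|---|---|
| Baseline only | 3.62 | 4.51 | 20% |
| EOT Chalder with no effect, IgG 1 SD | 3.72 | 4.43 | 16% |
| same, IgG 2 SD | 4.10 | 4.56 | 10% |
| same, IgG 4 SD | 4.30 | 4.49 | 4% |
| EOT Chalder, full effect | 4.08 | 4.46 | 9% |
| same, plus IgG 2 SD | 4.25 | 4.46 | 5% |
| same, plus IgG 4 SD | 4.38 | 4.48 | 2% |
| EOT and month-1 Chalder, full effect | 4.25 | 4.51 | 6% |
| Chalder at EOT, months 1, 4, 6 | 4.31 | 4.46 | 3% |
| same, plus IgG 2 SD | 4.38 | 4.47 | 2% |

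A true effect of 3.3 gives the same percentages within 1 point (baseline only: 2.69 v 3.34). A true effect of 0 gives −0.01 both ways. With 6 of 66 missing, the loss is about 9% at most (4.02 v 4.44). Complete-case means lie between 4.43 and 4.56.

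Varying the assumed correlation from 0.3 to 0.8 in the large-sample formula, with equal correlation between all visits, gives 3.90 to 4.14 with EOT Chalder only and 4.20 to 4.37 with EOT and months 1, 4 and 6.

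**Step 4: are the helpful outcomes secured?** Counted by visit, the scheduled clinical scores are Chalder 5, PCFS 4, SF-36 5, Fluge 16, PEM 5, Bell 5, COMPASS 4 (as one total), Schellong 2, grip 2, 6MWT 1, MoCA 1, SDMT 1, PROMIS-29 28 and PROMIS cognition 1. That is 80, including the Day-60 Chalder target itself, against 35 + 18 = 53 patients expected with Day-60 data. An ordinary regression cannot hold them all, and the SAP does not say which stay.

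**The case against.** The strongest reply is that the outcomes on the list already include stand-ins for treatment. Table 5 counts Chalder at EOT and months 1, 4 and 6, and the biomarker endpoints include "immunostatus (differential blood, IgG, IgM, IgA fractions) in blood at EOT, at month 2 and 6 after IA completion"; Table 1 schedules "Blood samples for immunoglobulin titers (IgA, IgG, IgM") at EOT as well. An immunoglobulin adsorber should separate the arms on these. Patients who stop early still have the EOT examinations, so most of the full analysis set should have some post-treatment data. This stands, and it is why 20% is an upper bound. Using IgM and IgA as well as IgG could reduce the loss further. But the stand-ins reduce the bias without removing it: IgG separated by only 1 SD still leaves 16%. The SAP also allows that "If treatment needs to be terminated, the EOT can occur as early as day 2", after fewer cycles, when the values may say little about arm.

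The 20% is an overall drop-out rate for a study that runs to Day 180, so Day-60 missingness may be lower. That also stands, and the loss shrinks in proportion.

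Section 4 calls the trial exploratory, the bias is conservative, and at 0.1 to 0.9 points it is small beside a half-width of about 3. All true. Yet section 9.2 labels this analysis confirmatory. The complete-data analysis may show a discrepancy, but it does not replace the primary estimate.

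The predictor count depends on how scores are split (Table 5 announces five Fluge domains but names four, and scores COMPASS by domain), and no size is claimed for it. Reading the list as Day-60 values only, which would discard EOT and month 1, fits poorly with Table 5.

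**Conclusion.** The concern holds. Section 8 as written omits treatment group from the imputation model of an analysis whose purpose is to estimate the treatment effect. The direction is certain when the effect is real and Day-60 scores are missing.

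The size is not fixed by the SAP. It depends on how many Day-60 scores are missing, when patients leave and which auxiliaries are kept. If 20% are missing completely at random, equally across arms, the loss runs from about 2% to 20% of the effect, or 0.1 to 0.9 points for a true effect of 4.5. The correlations and the IgG separation are assumed. This should be corrected before analysis. It does not threaten the type I error.

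**What to change.** State in section 8 that treatment group is a predictor in every imputation model. For the primary outcome, list the predictors, for example: *Missing Day-60 Chalder scores are imputed from treatment group, baseline Chalder, Chalder at EOT and months 1, 4 and 6, age, sex and BMI.* Name any further auxiliary, such as EOT IgG, instead of relying on all outcome variables.

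Imputing separately within arm would also remove the bias. With about 18 sham patients expected to have Day-60 data, arm as a predictor is likely to be the steadier choice; that is a judgement and was not simulated.

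Cost: SAP wording and one change to the mice predictor matrix. No new data are needed.
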